Subjects in Cohorts 2A and 2B and Cohorts 3A and 3B will receive a second single dose of CD388 Injection or placebo after washout of 5 effective half-lives after the first dose if it is determined that the safety and tolerability of the first dose is acceptable upon review of the cumulative safety data. Immediately prior to the second single dose, within each dose and route, any dropouts in the sentinel groups will be randomly replaced with subjects from the main groups, retaining their original treatment assignment (i.e., subjects assigned to placebo will remain placebo, and subjects assigned to CD388 will remain CD388; this may require unblinded personnel to oversee).

The PI and Sponsor will review blinded safety data after the initial sentinel group subjects at a dose level have completed dosing and followed for the minimum observation period as determined during the first single dose. If no drug-related SAEs or drug-related Grade ≥ 3 AEs have occurred, the subjects in the corresponding main group may be dosed within 24 hours.

The dose escalation scheme is presented in [Section 1.2](#).

The Schedule of Events is presented in [Table 1](#) (first single dose, Cohorts 1A, 1B, 2A, 2B, 3A, 3B), [Table 2](#) (second single dose, Cohorts 2A, 2B, 3A, and 3B), and [Table 3](#) (single dose, Cohort 4B). All subjects will be admitted to the clinical research unit (CRU) for observation and safety assessments from Day -1 (check-in) to Day 30. Subjects will be monitored for AEs (including reactogenicity/injection site reactions and hypersensitivity reactions) and SAEs as indicated below:

Cohort	AE/SAE monitoring period from signing of ICF:
1A, 1B	Through 4 months after the dose of study drug
2A, 2B, 3A, 3B, 4B	Through 205 days after the last dose of study drug (Day 206 ±10 days)

Abbreviation: ICF = informed consent form.

Safety will also be assessed by physical examinations, ECGs, vital signs measurements, and laboratory evaluations (hematology, coagulation, serum chemistry, and urinalysis) at various time points during and after the CRU stay. Concomitant medication use will be recorded throughout the study.

Continuous 12-lead digital ECG recording will be performed using a 12-lead Holter ECG monitor as indicated below:

Cohort	Holter Monitoring Period
1A, 1B	1 hour before administration of study drug until 48 hours after dosing
2A, 2B, 3B	1 hour before first administration of study drug until 48 hours after dosing ^a

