7.4. Subject Withdrawal Criteria

7.4.1. Subject Stopping Rules

Subjects in Cohorts 2A, 2B, 3A, and 3B will be followed through Outpatient Visit 4 (OV4) of the first dosing period, and will not receive the second single dose:

- If the subject develops anaphylaxis or a related Grade 3 or Grade 4 AE
- If the subject has a persistent (i.e., >5 days with no response to treatment) Grade ≥ 2 rash considered related to the investigational drug by the Principal Investigator ([Appendix 4](#))
- If the Investigator believes that it is in the best interest of the subject to not receive a second dose
- If the subject no longer meets all eligibility criteria prior to the second single dose
- If the subject becomes pregnant prior to the second single dose

If a subject is removed from the study for any reason, the subject will be followed for resolution of any ongoing AE(s).

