- An unscheduled visit for initial rash evaluation (day 1 of the rash) is required.
- Assessment of safety blood samples by the local laboratory is required. A copy of the local laboratory report should be anonymized and will be retrieved by the monitor.

- Digital pictures should be taken within 24 hours after the onset of the rash.
- Referral to a dermatologist is only needed if the rash diagnosis is uncertain (preferably within 24 hours after the onset of the rash). A copy of the dermatologist's report should be anonymized and will be retrieved by the monitor.
- Cetirizine, levocetirizine, topical corticosteroids, or antipruritic agents may be prescribed.
- The description of the rash should be reported per 'Unscheduled Visit in Case of Rash' in the eCRF (i.e., the initial rash assessment pages).

For close follow-up of the rash, unscheduled visits will also be performed 1 and 7 days after the initial assessment of the rash. At these visits, safety blood samples and digital pictures should be taken. The follow-up rash assessment pages of the eCRF should be completed for all follow-up visits. For these and all subsequent local laboratory blood sample assessments: a copy of the local laboratory reports should be anonymized and will be retrieved by the monitor.

If the rash is unresolved after 7 days, additional unscheduled visits may be performed at the Investigator's discretion. Upon resolution/stabilization of the rash, digital pictures should be taken and the final rash assessment pages of the eCRF should be completed.

The subject should be advised to contact the Investigator immediately if there is any worsening of the rash, if any systemic signs or symptoms appear, or if mucosal involvement develops.

In case the rash evolves from a Grade 1 to a higher grade, additional unscheduled visits have to be conducted according to the guidelines for Grade 2 or Grade 3–4 rash, respectively.

Grade 2 Rash

A Grade 2 rash is defined as **diffuse, maculopapular rash OR dry desquamation**.

- Subjects will permanently discontinue the intake of study drugs and be withdrawn from the study. No rechallenge is allowed.

Note: Subjects experiencing Grade 2 rash following the last intake of study drug may continue in the study as long as they are not re-exposed to suspect study drug.

- An unscheduled visit for initial rash evaluation (day 1 of the rash) is required.

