- **vesiculation, moist desquamation, or ulceration** OR
- **cutaneous event with one of the following** (revised by the Sponsor):
 - elevations in AST/ALT more than 2× baseline value and $\geq 5 \times$ ULN
 - fever $>38^{\circ}\text{C}$ or 100°F
 - eosinophils $>1000/\text{mm}^3$
 - serum sickness-like reaction

A Grade 4 rash is defined as:

- **exfoliative dermatitis** OR
- **a generalized rash with mucous membrane involvement** OR
- **erythema multiforme** OR
- **Stevens-Johnson Syndrome** OR
- **rash associated with necrosis requiring surgery**

- Subjects will **permanently discontinue** the intake of all study drug(s) and be withdrawn from the study with Grade 3 or 4 rash identified. No rechallenge is allowed.
- An unscheduled visit for initial rash evaluation (day 1 of the rash) is required.
- Assessment of safety blood samples by the local laboratory is required on the day of initial rash evaluation and the day thereafter (days 1 and 2 of the rash), and as indicated below. A copy of the local laboratory report should be anonymized and will be retrieved by the monitor.
- Digital pictures should be taken within 24 hours after the onset of the rash and on day 1 of the rash, and as indicated below.
- Referral to a dermatologist is required, preferably within 24 hours after the onset of the rash. A copy of the dermatologist's report should be anonymized and will be retrieved by the monitor.
- A biopsy should be performed within 24 hours after the onset of the rash. A copy of the biopsy report should be anonymized and will be retrieved by the monitor.
- Appropriate management should be undertaken and subjects should be followed until resolution of the rash.
- The description of the rash should be reported per 'Unscheduled Visit in Case of Rash' in the eCRF (i.e., the initial rash assessment pages). The follow-up rash assessment pages of the eCRF should be completed for all follow-up visits.

For close follow-up of the rash, unscheduled visits will be performed as follows:

- Follow-up visits on days 2, 3, and 4 of the rash are required. Additional safety blood samples and digital pictures are to be taken on these days only if the subject's AST/ALT on day 1 and/or day 2 of rash $>2\times$ baseline value, and/or $\geq 5 \times$ ULN and/or in case of rash progression. For these and all subsequent local laboratory blood sample assessments: a copy of the local laboratory report should be anonymized and will be retrieved by the monitor.

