APPENDIX 5. VISIT SCHEDULE FOR RASH MANAGEMENT FOR ADULT SUBJECTS

This visit schedule summarizes the visits and assessments to be performed in case of rash. At the Investigator's discretion, additional visits and assessments may be performed. For all rashes, please also complete the specific rash assessment pages of the eCRF for all visits. Local laboratory blood sample assessments will be documented/collected as described in the text above.

Rash Day	Grade 1 Rash	Grade 2 Rash	Grade 3 or 4 Rash
Rash day 1 ^a	
 Study drug(s) MAY be CONTINUED. Unscheduled visit for initial rash evaluation REQUIRED. Assessment of safety blood sample by local laboratory REQUIRED. Digital pictures REQUIRED (within 24 h). Referral to dermatologist ONLY IF rash diagnosis uncertain (within 24 h). 	
 Study drug(s) MUST be permanently DISCONTINUED if the subject has a persistent (i.e., >5 days with no response to treatment) Grade ≥ 2 ^b rash considered related to CD388 by the Investigator. Rechallenge is NOT ALLOWED. Unscheduled visit for initial rash evaluation REQUIRED. Assessment of safety blood sample by local laboratory REQUIRED. Digital pictures REQUIRED (within 24 h). Referral to dermatologist REQUIRED (within 24 h). Biopsy IF ADVISED by dermatologist (within 24 h). 	
 Study drug(s) MUST be permanently DISCONTINUED. Rechallenge is NOT ALLOWED. Unscheduled visit for initial rash evaluation REQUIRED. Assessment of safety blood sample by local laboratory REQUIRED. Digital pictures REQUIRED (within 24 h). Referral to dermatologist REQUIRED (within 24 h). Biopsy REQUIRED (within 24 h).
Rash day 2	
 Follow-up visit REQUIRED. Assessment of safety blood sample by local laboratory REQUIRED. Digital pictures REQUIRED. 	
 Follow-up visit REQUIRED. Assessment of safety blood sample by local laboratory REQUIRED. Digital pictures REQUIRED. 	
 Follow-up visit REQUIRED. Assessment of safety blood sample by local laboratory REQUIRED. Digital pictures REQUIRED.

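### A drug-related Grade 2 rash after the first dose has no single rule for the second dose: Appendix 4 bars re-exposure outright, while Section 7.4.1, the synopsis and Appendix 5 require a stop only when the rash persists

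*Protocol*

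**What the plan says.** Subjects in Cohorts 2A, 2B, 3A and 3B are planned to receive a second dose. Four places in the protocol bear on whether a subject with a drug-related Grade 2 rash after the first dose may have it.

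- **Appendix 4, Grade 2:** "Subjects will permanently discontinue the intake of study drugs and be withdrawn from the study. No rechallenge is allowed". No minimum duration or treatment response is mentioned. A note allows a subject whose rash follows the last intake to stay in the study, but still without re-exposure.
- **Section 7.4.1, rash bullet:** "If the subject has a persistent (i.e., >5 days with no response to treatment"), applied to related rashes of Grade 2 or higher and citing Appendix 4. The consequence for the subject is different: subjects "will be followed through Outpatient Visit 4 (OV4) of the first dosing period, and will not receive the second single dose".
- **Synopsis, Subject Stopping Rules:** the same condition as 7.4.1.
- **Appendix 5, Grade 2 column, rash day 1:** "Study drug(s) MUST be permanently DISCONTINUED if the subject has a persistent (i.e., >5 days with no response to treatment"). A separate sentence then rules out rechallenge.

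For Grade 3 or 4 the texts agree on dosing. The first bullet of 7.4.1 reads "If the subject develops anaphylaxis or a related Grade 3 or Grade 4 AE", and the Grade 3–4 column of Appendix 5 reads "Study drug(s) MUST be permanently DISCONTINUED. Rechallenge is NOT ALLOWED". Appendix 4 also stops the drug, but adds that these subjects will "and be withdrawn from the study with Grade 3 or 4 rash identified".

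**The concern.** Because related Grade 3 and 4 events are already stopped unconditionally, the persistence condition has practical effect only at Grade 2, and that is where Appendix 4 omits it. A site working from 7.4.1 and Appendix 5 could give a second dose to a subject whom Appendix 4 says must not be rechallenged.

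At stake is whether a healthy volunteer who has had a drug-related diffuse rash is re-exposed to a long-acting Fc-conjugate in a first-in-human study. The automatic safety gates do not reach this case. Release of the main group (Section 6.1) depends on drug-related SAEs or drug-related events of Grade 3 or higher. The study halt (Section 7.6) needs two subjects with the same Grade 3 event or one with a Grade 4 event.

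There is also a reporting consequence. Section 5 includes events leading to drug discontinuation or study withdrawal in the safety endpoints, and SAP Table 6 tabulates the two separately. The same Grade 2 rash could count as both (Appendix 4), as discontinuation only (7.4.1, if persistent) or as neither (7.4.1, if short or responsive).

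**Working it through.** There is no plan figure to reproduce. The check sets the texts side by side for a drug-related rash after dose 1 and asks what each requires for dose 2.

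| Rash after dose 1 | Appendix 4 | 7.4.1 and synopsis | Appendix 5 |
|---|---|---|---|
| Grade 2, clears in 4 days | Dose 2 barred | Rash stop not triggered | Mandatory discontinuation not triggered |
| Grade 2, more than 5 days, responds to treatment | Dose 2 barred | Rash stop not triggered | Mandatory discontinuation not triggered |
| Grade 2, more than 5 days, no response | Dose 2 barred | Dose 2 barred | Dose 2 barred |
| Grade 3 or 4 | Dose 2 barred | Dose 2 barred (first bullet) | Dose 2 barred |

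The texts diverge in the first two rows. The gap is not limited to short rashes, because the condition has two parts (duration and lack of response) and failing either one avoids the stop.

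Three features of the text keep the ambiguity open:

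1. Section 7.4.1 refers the reader to Appendix 4 but uses a threshold that Appendix 4 does not contain.
2. Appendix 4 describes Appendix 5 as a full summary of the same guidelines, yet the two differ on this rule.
3. Appendix 5 places the persistence test under rash day 1, when persistence beyond five days cannot yet be known.

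**Follow-up.** Appendix 4 withdraws the subject (Grade 2, and separately Grade 3–4). Section 7.4.1 keeps the subject to OV4 of the first period. The Appendix 4 note on rash after the last intake partly reconciles this at Grade 2, but there is no such note at Grade 3–4.

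**Scope (Table 5).**
- Subjects planned for dose 2: 4 cohorts × (2 sentinel + 9 main) = 4 × 11 = 44.
- On CD388: 4 × (1 + 7) = 4 × 8 = 32.
- Section 4.3 reports 66 subjects dosed at 50, 150 or 450 mg. Six cohorts × 11 = 66, so first dosing of all 44 was complete when this text was written.
- No rash count is given and the documents do not say whether dose 2 had been given, so no rash rate or probability is assumed.

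**The case against.** The strongest reply is that the texts can all be obeyed at once. Section 7.4.1 lists sufficient reasons to withhold dose 2. It does not say that persistence is the only rash stop or that dose 2 must otherwise be given. A site applying the stricter Appendix 4 breaches nothing. That is correct, and it favours the stricter rule as the fix. It does not show that a site would find that rule, because no text gives Appendix 4 precedence and the explicit condition in Appendix 5 invites the opposite reading.

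Other points carry some weight:

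- **The rechallenge sentence in Appendix 5** may stand alone, as it does in the Grade 3–4 column. It may also depend on the conditional sentence before it. The ambiguity is part of the problem.
- **The eligibility recheck before dose 2** could exclude the subject through exclusion 2a, which covers a history of skin rashes. Read that way it would also bar Grade 1 rash, which Appendix 4 leaves to the Investigator's discretion, and it would make the rash bullet in 7.4.1 redundant.
- **General safeguards remain.** Section 6.1 allows dose 2 only "if it is determined that the safety and tolerability of the first dose is acceptable upon review of the cumulative safety data". Appendix 4 has all rashes discussed between Investigator and Sponsor. Section 6.2.1 permits a work-up and a change of dose or route after a related event of Grade 2 or higher. Section 7.4.1 gives the Investigator discretion. These make inappropriate re-dosing less likely, but they rest on judgement and none sets a Grade 2 rule.
- **Follow-up is partly protected.** Table 1 asks for OV4 procedures on early discontinuation and Section 7.4.2 encourages them. Intervening PK and ADA visits could still be lost.
- **The sponsor may intend the persistence rule**, since three of the four places state it. If so, it should be written into Appendix 4 as well. One rule is needed in either case.

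**Conclusion.** The inconsistency is real and bears on subject safety. A related Grade 2 rash after dose 1 that is short, or that responds to treatment, is barred from re-exposure by Appendix 4 and meets no mandatory rash stop in 7.4.1, the synopsis or Appendix 5. It should be corrected. It is not a fundamental flaw, because other safeguards remain and Section 4.3 reports no concerning observation on blinded review of first dosing.

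The figure of 44 subjects (32 on CD388) is the number the rule governs, not the number affected, which is unknown and probably small. Withholding dose 2 for any related rash of Grade 2 or higher is the only dosing rule that is compatible with all four texts as they stand. The conclusion rests on comparing the wording and needs no assumed rash rate.

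**What to change.** State one rule in Section 7.4.1, the synopsis and Appendices 4 and 5: any related rash of Grade 2 or higher after dose 1 means no second dose, and the subject is followed through OV4 instead of being withdrawn.

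- In 7.4.1 and the synopsis, delete the persistence condition from the rash bullet.
- In the Grade 2 column of Appendix 5, delete the conditional clause so that discontinuation is unconditional.
- In Appendix 4 (Grade 2 and Grade 3–4), replace withdrawal after dose 1 with follow-up through OV4.
- When clearing subjects for dose 2, apply the rule to any related rash already recorded after dose 1.

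The cost is wording in four places, with no new procedure. The downside is the possible loss of a repeat-dose subject: one CD388 subject withheld takes that cohort's repeat-dose CD388 group from 8 to 7 (1/8 = 12.5%). The analysis is descriptive with no hypothesis testing, and the subject's dose-1 data through OV4 are kept.

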APPENDIX 5. VISIT SCHEDULE FOR RASH MANAGEMENT FOR ADULT SUBJECTS

This visit schedule summarizes the visits and assessments to be performed in case of rash. At the Investigator's discretion, additional visits and assessments may be performed. For all rashes, please also complete the specific rash assessment pages of the eCRF for all visits. Local laboratory blood sample assessments will be documented/collected as described in the text above.

Rash Day	Grade 1 Rash	Grade 2 Rash	Grade 3 or 4 Rash
Rash day 1 ^a	
 Study drug(s) MAY be CONTINUED. Unscheduled visit for initial rash evaluation REQUIRED. Assessment of safety blood sample by local laboratory REQUIRED. Digital pictures REQUIRED (within 24 h). Referral to dermatologist ONLY IF rash diagnosis uncertain (within 24 h). 	
 Study drug(s) MUST be permanently DISCONTINUED if the subject has a persistent (i.e., >5 days with no response to treatment) Grade ≥ 2 ^b rash considered related to CD388 by the Investigator. Rechallenge is NOT ALLOWED. Unscheduled visit for initial rash evaluation REQUIRED. Assessment of safety blood sample by local laboratory REQUIRED. Digital pictures REQUIRED (within 24 h). Referral to dermatologist REQUIRED (within 24 h). Biopsy IF ADVISED by dermatologist (within 24 h). 	
 Study drug(s) MUST be permanently DISCONTINUED. Rechallenge is NOT ALLOWED. Unscheduled visit for initial rash evaluation REQUIRED. Assessment of safety blood sample by local laboratory REQUIRED. Digital pictures REQUIRED (within 24 h). Referral to dermatologist REQUIRED (within 24 h). Biopsy REQUIRED (within 24 h).
Rash day 2	
 Follow-up visit REQUIRED. Assessment of safety blood sample by local laboratory REQUIRED. Digital pictures REQUIRED. 	
 Follow-up visit REQUIRED. Assessment of safety blood sample by local laboratory REQUIRED. Digital pictures REQUIRED. 	
 Follow-up visit REQUIRED. Assessment of safety blood sample by local laboratory REQUIRED. Digital pictures REQUIRED.
Rash day 3	No Rash follow-up visit required ^c	No Rash follow-up visit required ^c	
 Follow-up visit REQUIRED. Assessment of safety blood sample by local laboratory and digital pictures REQUIRED only if on days 1 and/or 2 of rash AST/ALT $>2\times$ baseline value, AND/OR $5 \times$ ULN, AND/OR in case of rash progression.
Rash day 4	No Rash follow-up visit required ^c	No Rash follow-up visit required ^c	
 Follow-up visit REQUIRED. Assessment of safety blood sample by local laboratory and digital pictures REQUIRED only if on days 1 and/or 2 of rash AST/ALT $>2\times$ baseline value, AND/OR $5 \times$ ULN, AND/OR in case of rash progression.

Rash Day	Grade 1 Rash	Grade 2 Rash	Grade 3 or 4 Rash
Rash day 5	No Rash follow-up visit required ^c	No Rash follow-up visit required ^c	
 Follow-up visit REQUIRED. Assessment of safety blood sample by local laboratory and digital pictures REQUIRED only if on days 1 and/or 2 of rash AST/ALT $>2 \times$ baseline value, AND/OR $5 \times$ ULN, AND/OR in case of rash progression.
Rash day 6	No Rash follow-up visit required ^c	No Rash follow-up visit required ^c	
 Follow-up visit REQUIRED. Assessment of safety blood sample by local laboratory REQUIRED. Digital pictures REQUIRED.
Rash day 7	No Rash follow-up visit required ^c	No Rash follow-up visit required ^c	No Rash follow-up visit required
Rash day 8	
 Follow-up visit REQUIRED ^c Assessment of safety blood sample by local laboratory REQUIRED. Digital pictures REQUIRED. 	
 Follow-up visit REQUIRED ^c Assessment of safety blood sample by local laboratory REQUIRED. Digital pictures REQUIRED. 	No Rash follow-up visit required

Table 11	PCS Values for Coagulation.....	27
Table 12	PCS Values for Urinalysis.....	28
Table 13:	PCS Values for Vital Signs	28

ABBREVIATIONS

ADA	Anti-Drug Antibodies
AE	Adverse Event
ANOVA	Analysis of Variance
ATC	Anatomical Therapeutic Chemical
BMI	Body Mass Index
CI	Confidence Interval
CRF	Case Report Form
CRU	Clinical Research Unit
CSF	Cerebrospinal Fluid
CSR	Clinical Study Report
CV%	Coefficient of Variability
DAR	Drug-Antibody Ratio
DMP	Data Management Plan
DSMB	Data Safety Monitoring Board
DTS	Deviation Tracking System
ECG	Electrocardiogram
FIH	First-In-Human
EOS	End of Study
ET	Early Termination
GMR	Geometric Mean Ratio
ICF	Informed Consent Form
ICH	International conference on council for harmonisation
IM	Intramuscular
IP	Investigational Product
LN	Natural Log
LSMEAN	Least Squares Mean
MEDDRA	Medical Dictionary for Regulatory Activities
NCA	Non-Compartmental Analysis
NP	Nasopharyngeal
PCS	Potentially Clinically Significant
PK	Pharmacokinetic(s)
PT	Preferred Term
SAD	Single Ascending Dose
SAE	Serious Adverse Event
SAP	Statistical Analysis Plan
SD	Standard Deviation
SOC	System Organ Class
SOP	Standard Operating Procedure
SQ	Subcutaneous

TEAE	Treatment-emergent Adverse Event
TFLS	Tables, Figures, and Listings
WHO-DD	World Health Organization Drug Dictionary

1 INTRODUCTION

This statistical analysis plan (SAP) provides a detailed description of the statistical methods and procedures to be implemented for the analyses of data from Protocol No. CD388.IM.SQ.1.01.

Pre-planning of analyses reduces the potential for bias and often reduces disputes between sponsor and the regulatory authority regarding the validity of the results. The same principles apply to supportive and/or sensitivity analyses. These analyses must be prospectively specified. (Good Review Practice: Clinical Review of Investigational New Drug Applications, December 2013).

The analyses described in the SAP are based upon the final protocol version Amendment 2 dated 2023-02-07.

